	8.2.4.4. Subgroup Analysis					
	- It was described that risk ratio and risk difference will not be calculated for concomitant					
	use of steroids or immunosuppressants other than steroids.					
	9. LISTINGS					
	- Listings of the occurrence of adverse drug reactions in children, elderly, patients with					
	hepatic dysfunction, and patients with renal dysfunction were added.					
	Other description adjustments were made.					

2. INTRODUCTION

This statistical analysis plan describes the statistical analysis plan for the special investigation of Vfend. In this plan, sentences cited from the Protocol are shown in *Italics*.

2.1. Study Design

This study is a prospective multicenter cohort study conducted in patients receiving this product. Pediatric and adult patients who were treated with this product for the purpose of prophylactic administration of this product for invasive fungal infections (IFI) at the commencement of treatment with this product will be included in the study. The observation period shall start on the day of initiation of Vfend treatment and end on the day of completion of treatment; provided that the patients will be followed until the last day of the study period as long as possible if the treatment prolongs. The target sample size is set to be 200 patients in total, 100 patients each for children and adults. The rationale for target sample size is shown below. With hepatic toxicity and visual events considered as major investigation items, tally the occurrence status for patients who developed events related to major investigation items and evaluate the differences in patient background, dose, etc. between patients who can continuously receive treatment with this product and patients who must discontinue treatment with this product.

Rationale for sample size

The sample size is 100 patients each for children and adults, 200 patients in total.

Safety perspectives:

In the phase 3 study of prophylactic administration of Vfend in foreign patients with HSCT (study A1501073), the incidence of adverse reactions classified into the SOC of hepatobiliary disorders was 20.2% (47/233 patients). Of those, one patient was led to discontinuation of treatment with this product. In the phase 3 study of secondary prophylactic administration of Vfend in foreign patients with HSCT (study A1501038), the incidence of adverse reactions classified into the SOC of hepatobiliary disorders was 24.4% (11/45 patients). Of those, two patients were led to discontinuation of treatment with this product. Also, in the clinical study of Vfend conducted in Japanese children (from 2 years old to under 15 years old) (study A1501096), the incidence of adverse reactions related to hepatotoxicity including abnormal hepatic function test values was 19.0% (4/21 patients). Of those, two patients were led to discontinuation of treatment with this product. Based on the above, the incidence of hepatotoxicity in patients treated with this product for prophylaxis of mycosis was similar between the Japanese and foreign patients and it was considered that such incidence is also similar between adults and children.

In the case where the number of patients to be collected for the special investigation for prophylactic administration of Vfend for invasive fungal infections is set to be 200 patients and the incidence of hepatotoxicity is presumed to be 20%, it was estimated that at least 31 patients with hepatotoxicity will be accumulated at a probability of about 95%. With the cumulation of this sample size, it was considered possible to compare and review the proportion of patients who discontinue the treatment with this product with other clinical studies.

Although the incidence of visual events varies among different studies (study A1501073: 12.0%, study A1501038: 4.4%, and study A1501096: 42.9%), if it is presumed that there is the incidence of 5% or higher, the expected value of the incidence to be observed in 200 patients will be at least 10 patients. While it is possible that there may be no patient who discontinues the treatment with this product due to visual events based on the results of clinical studies, if any patient who discontinues the treatment with this product is observed, how it happened will be examined.

Effectiveness perspectives:

The successful rate of prophylaxis at Day 100 in the phase 3 study of prophylactic administration (study A1501073) was 54.3% (121/223 patients) and the successful rate of prophylaxis at Day 180 was 48.9% (109/223 patients). Presuming that the 50% prophylactic effect can be obtained at Day 180 by referring to the above results, the 95% CI will be 40-60% if the target sample size is set to be 100 patients and 43-57% if the target sample size is set to be 200 patients. The prophylactic effect can be confirmed at the estimate accuracy of about $\pm 10\%$ if 100 patients for whom this product is administered for prophylaxis are accumulated and that of about $\pm 7\%$ if 200 patients are accumulated.

2.2. Study Objectives

This surveillance is intended to grasp the following items, etc. for the safety and effectiveness of this product in daily clinical practice for prophylactic administration of this product for invasive fungal infections in pediatric and adults and review the necessity for further special investigation and post-marketing clinical study.

- Unknown adverse reactions including the time of long-term use
- Occurrence of adverse reactions under actual clinical settings
- Factors considered to affect the safety and effectiveness of this product

3. INTERIM AND FINAL ANALYSES

In this study, interim analyses for periodic safety report will be performed periodically. At the time of interim analyses, only the analyses of items necessary for periodic safety update report among the statistical analyses specified in this plan will be performed. In addition, the final analysis for the application for reexamination will be performed. At the time of the final analysis, all analyses specified in this plan will be performed.

4. HYPOTHESIS AND DECISION RULES

4.1. Statistical Hypothesis

Because this study is not a confirmatory investigation, the tests are considered as exploratory tests. The P value of test results will be evaluated as descriptive statistics. The significance level is not provided, but a threshold may be set afterwards for the purpose of screening.

4.2. Statistical Decision Rules

Not applicable

5. ANALYSIS SETS

5.1. Safety Analysis Set

The safety analysis set is defined as the full analysis set that is as close as possible to all patients treated with Vfend. More specifically, the safety analysis set is defined as the population of patients registered or reported, excluding patients who meet at least one of the following conditions:

- a. The case report form could not be collected at all (description in the report, "case report form not collected")
- b. There was a violation or deficiency in the contract (description in the report, "contract violation/deficiency")
- c. There was a violation of registration (description in the report, "registration violation")
- d. Administration of the drug under investigation is not reported at all (description in the report, "no administration information")
- e. Information on adverse events is not reported at all no visits after the first prescription day (description in the report "no adverse event information no revisits")
- f. Information on adverse events is not reported at all there is a visit after the first prescription day but no description of safety information (description in the report, "no adverse event information no description")

"Guidance for Criteria for Inclusion in Analysis Sets and Data Handling in Drug Use Investigations" will be followed for the details of each criterion.

5.2. Effectiveness Analysis Set

The effectiveness analysis set is defined as the population of patients in the safety analysis set, excluding patients who meet at least one of the following conditions:

- g. Effectiveness assessment is not reported at all (description in the report, "no information on effectiveness")
- h. Disease other than the target diseases of the study (description in the report, "non-target disease")

5.3. Other Analysis Sets

Not applicable

5.4. Subgroup Analysis

Subgroup analyses of safety and effectiveness will be performed for the following patient background factors and other factors. Levels in parentheses are levels of subgroups, and underlined levels are the reference for calculation of risk ratio and risk difference.

- Sex [male, female]
- Age (1) [<15 years, ≥ 15 years]
- Age (2) [<65 years, ≥65 years)
- Age (children 1) [newborns (<1 month after birth), infants (≥1 month to <1 year), younger children (≥1 to <7 years), children (≥7 to <15 years)]
- Age (children 2) [<2 years, ≥ 2 to <15 years]
- Hospitalized Status [inpatient, outpatient]
- Objective of treatment [primary prophylaxis (patients without history of fungal infection), secondary prophylaxis (patients with history of fungal infection), others]
- Type of transplantation [autograft, allogeneic full transplantation, allogeneic mini-transplantation]
- Source of transplantation [bone marrow, cord blood, peripheral stem cell]
- Occurrence of GVHD (graft versus host disease) [absent, present]
- Indication for transplantation¹ [leukemia, myelodysplastic syndrome, malignant lymphoma, myeloma, others]
- Severity of indication for transplantation [mild, moderate, severe]
- Hepatic dysfunction [absent, present]
- Severity of hepatic dysfunction [mild, moderate, severe]
- Renal dysfunction [absent, present]
- Severity of renal dysfunction [mild, moderate, severe]
- Past medical history [absent, present]
- Concurrent illness [absent, present]
- Congenital severe immunodeficiency² [absent, present]
- White blood cell count before administration [$<3000/\mu$ L, $\geq 3000/\mu$ L]
- Neutrophil count before administration [$<500/\mu$ L, $\geq 500/\mu$ L]
- Concomitant use of broad-spectrum antibiotics [absent, present]
- Use of contraindicated concomitant medications [absent, present]
- Use of concomitant medications requiring precautions for coadministration [absent, present]
- Concomitant use of immunosuppressants (other than steroids) [absent, present]
- Concomitant use of steroids [absent, present]
- Concomitant use of steroids or immunosuppressants other than steroids [absent, present]
- Concomitant use of other antifungal agents [absent, present]
- Prior treatment (antifungal agents administered for prophylaxis of invasive fungal infections)
 [absent, present]
- Long-term treatment [$\leq 180 \text{ days}$, $\geq 180 \text{ days}$]
- Duration of treatment with Vfend (<30 days, \geq 30 to <60 days, \geq 60 to <90 days, \geq 90 to <120 days, \geq 120 to <150 days, \geq 150 to <180 days, \geq 180 days)

¹: Indication will be classified in reference to the Japanese Society of Hematology Guideline for Hematological Malignancies (http://www.jshem.or.jp/gui-hemali/table.html).

²: Congenital severe immunodeficiency is defined as a complication included in MedDRA HLGT "congenital immune system disorders" and "immunodeficiency syndrome" (primary and secondary).

Patients who may meet contraindications in the package insert of Vfend (hereinafter referred to as contraindicated patients) will be extracted based on separately specified criteria, and subgroup analyses of safety will be performed.

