# 7.5. Study size

#### 7.5.1. Planned sample size

200 patients (100 patients each for children and adults)

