Although the incidence of visual events varies among different studies (study A1501073: 12.0%, study A1501038: 4.4%, and study A1501096: 42.9%), if it is presumed that there is the incidence of 5% or higher, the expected value of the incidence to be observed in 200 patients will be at least 10 patients. While it is possible that there may be no patient who discontinues the administration of this product due to visual events based on the results of clinical studies, if any patient who discontinues the administration of this product is observed, how it happened will be examined.

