8.2.3.4. Subgroup Analysis

The number and proportion of patients who experienced at least one adverse drug reaction will be tabulated for each factor specified in Section 5.4. To evaluate the relationship between patient background factors and the development of adverse drug reactions, the analysis specified in Section 8.1.3 will be performed. Risk ratio and risk difference will not be calculated for concomitant use of steroids or immunosuppressants other than steroids.

The listing of adverse drug reactions will be prepared for contraindicated patients. The number and proportion of patients with adverse drug reactions will be tabulated by SOC and PT as necessary.

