8.2.4.4. Subgroup Analysis

To evaluate the relationship between patient background factors and effectiveness, subgroup analyses of the proportion of patients who developed invasive fungal infections and the proportion of patients with successful prophylaxis of invasive fungal infections will be performed in accordance with Section 8.1.3 for each of the factors specified in Section 5.4. Risk ratio and risk difference will not be calculated for concomitant use of steroids or immunosuppressants other than steroids.

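### The elderly factor Age (2) uses everyone under 65 as reference, a group planned to be more than half children, so its risk ratios and risk differences mix an elderly effect with a child–adult difference

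*SAP*

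**What the plan says.** SAP 5.4 lists the subgroup factors and states that "underlined levels are the reference for calculation of risk ratio and risk difference". For the elderly factor the underlined level is "Age (2) [ <65 years", compared with 65 years or over, in all patients. The target in SAP 2.1 is: "The target sample size is set to be 200 patients in total, 100 patients each for children and adults". Protocol 7.5.1 agrees.

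Age (2) is then used in several places:

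- **Safety, SAP 8.2.3.4:** "The number and proportion of patients who experienced at least one adverse drug reaction will be tabulated for each factor specified in Section 5.4", followed by "To evaluate the relationship between patient background factors and the development of adverse drug reactions, the analysis specified in Section 8.1.3 will be performed". Section 8.1.3 supplies an unadjusted risk ratio and risk difference, each with a 95% interval, and a graph of the risk ratio.
- **Effectiveness, SAP 8.2.4.4:** analyses of the IFI and success rates "will be performed in accordance with Section 8.1.3 for each of the factors specified in Section 5.4".
- **Proportions only:** the SOC/PT tables of all and of serious adverse drug reactions (8.2.3.1), and the IFI and success rates by age (8.2.4.1, 8.2.4.2).

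A three-level age (under 15, 15 to under 65, 65 or over) appears only in the background table of SAP 8.2.2. Age (1) splits at 15 and so pools the elderly with other adults. SAP 6.4 names no covariates. No planned estimate compares patients of 65 or over with those aged 15 to under 65.

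**The concern.** A factor that splits at 65 will be read as showing whether elderly patients fare differently from other adults. Here the comparator is a mixture whose larger part, by design, is children. If children have more events than adults aged 15–64, the reference rate rises and an elderly excess shrinks or disappears. If children have fewer, an elderly excess is inflated.

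This matters because finding factors that affect safety and effectiveness is a stated objective (Protocol 6, SAP 2.2), and the final analysis supports the re-examination application (SAP 3). The elderly also receive their own listing in SAP 9.

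**Working it through.** **Inputs**

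- Planned sample: 100 children and 100 adults (Protocol 7.5.1, SAP 2.1). I take children as under 15, because the adult age bands in SAP 8.2.2 start at 15.
- Number aged 65 or over, n: not given. Assumed range 10–40.
- Visual events (Protocol 7.5.2): "study A1501073: 12.0%, study A1501038: 4.4%, and study A1501096: 42.9" per cent. Study A1501096 is the paediatric study (2 to under 15 years). The other two are described as studies in foreign HSCT patients, so using 12.0% as the rate at 15–64 is an assumption.
- Hepatic toxicity (same section): 4/21 = 19.0% in the paediatric study, 47/233 = 20.2% and 11/45 = 24.4% in the foreign studies. These percentages reproduce.

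The plan states no figure for Age (2) itself. Its nearby claim of at least 31 hepatic cases in 200 patients at 20% incidence, with probability about 95%, also reproduces (exact binomial 0.957).

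**Formulas**

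Let w be the share of children in the reference, and p_c, p_a and p_e the rates in children, at 15–64 and at 65 or over.

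- w = 100 / (200 − n)
- Reference rate = w·p_c + (1 − w)·p_a
- Planned risk ratio = (p_e / p_a) × 1 / (1 − w + w·p_c/p_a)
- Planned risk difference = (p_e − p_a) − w·(p_c − p_a)

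The distortion vanishes only if p_c = p_a. Otherwise its sign follows p_c − p_a.

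**Illustration at the plan's rates, with an assumed true doubling in the elderly**

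Visual events: p_c = 42.9%, p_a = 12.0%, p_e = 24.0%. Hepatic toxicity: p_c = 19.0%, p_a = 20.2%, p_e = 40.4%. Against adults aged 15–64 the ratio is 2.00 for both.

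| n aged ≥65 | w | Visual: under-65 proportion | Visual: ≥65 minus <65 (points) | Hepatic: ratio ≥65 to <65 |
|---|---|---|---|---|
| 10 | 52.6% | 28.3% | −4.3 | 2.06 |
| 20 | 55.6% | 29.2% | −5.2 | 2.07 |
| 30 | 58.8% | 30.2% | −6.2 | 2.07 |
| 40 | 62.5% | 31.3% | −7.3 | 2.08 |

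For n = 20, visual: (100 × 42.9% + 80 × 12.0%) / 180 = (42.9 + 9.6) / 180 = 29.2%. The elderly proportion of 24% then looks lower than the reference, although it is twice that of other adults. For hepatic toxicity: (19.0 + 16.16) / 180 = 19.5%, and the ratio hardly moves.

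**How firm the visual illustration is**

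With n = 20, a true doubling reverses only if the child rate exceeds (24.0 × 180 − 80 × 12.0) / 100 = 33.6%. The denominator of the 42.9% is not given. If it is the 21 patients reported for hepatic toxicity (9/21), the exact 95% interval is 22–66%. At 22% the reference would be (22 + 9.6) / 180 = 17.6% and the ratio 24 / 17.6 = 1.37: attenuated, not reversed.

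**An endpoint that does receive a risk ratio: any adverse drug reaction (all rates assumed)**

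With n = 20, p_a = 40% and p_e = 60%, the true ratio is 1.50. The planned ratio is 2.08 if the child rate is 20%, 1.50 if it is 40%, 1.17 if it is 60% and 0.96 if it is 80%.

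**The case against.** The strongest reply has four parts.

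1. **The analysis is exploratory and correctly labelled.** SAP 4.1 treats P values as descriptive, and Age (2) is plainly under 65 versus 65 or over. This stands and limits the weight of the point. It does not make the comparison informative about the elderly.
2. **The 15–64 group can be recovered.** Age (1) and Age (2) are tabulated in parallel, so counts under 65 minus counts under 15 give counts at 15–64. This stands for the proportions. It does not correct the reported risk ratio, risk difference, intervals or graph.
3. **The plan's evidence on child–adult differences is mixed.** The hepatic rates are judged similar in adults and children, and the distortion there is negligible. The visual-event gap compares different studies and populations, and one of them appears small. This stands, and is why the visual figures are illustration only.
4. **The risk ratio may not be computed.** Under SAP 8.1.3 it is omitted if a category has five patients or fewer. If so few elderly patients are enrolled, only the tabulated proportions are affected.

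**Conclusion.** The point holds as a flaw in how the reference group is defined. Under the planned enrolment, children make up about 53–63% of the Age (2) reference for 10–40 elderly patients. The planned risk ratios and risk differences for any adverse drug reaction and for the IFI and success rates can then be biased in either direction. How much, and which way, cannot be said: the documents give no child and adult rates for these endpoints, and actual enrolment may differ from plan.

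A reader might infer more than this, without support from the documents:

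- **That the report will show visual-event risk ratios pointing the wrong way, or ratios that cross the 0.5 screen.** With no elderly effect, the visual rates would give 12 / 29.2 = 0.41, but no such ratio is planned. Visual events meet Age (2) only as proportions in the SOC/PT tables.
- **That a false or missed crossing of the screen (2 or more, 0.5 or less) would distort the safety follow-up.** In SAP 8.2.3.5 it triggers an SOC/PT table by that factor, and 8.2.3.1 already requires that table for Age (2). For effectiveness it affects only a listing (8.2.4.5).
- **That an elderly effect has been shown to be hidden or reversed.** Reversal needs a sufficiently higher child rate, which is not documented for any endpoint with a planned ratio.

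**What to change.** In SAP 5.4, compute the Age (2) risk ratio and risk difference in patients aged 15 or over only, with 15 to under 65 as reference. Wherever Age (2) is tabulated (8.2.3.1, 8.2.3.4, 8.2.4.1, 8.2.4.2, 8.2.4.4), show the three levels already in SAP 8.2.2: under 15, 15 to under 65, 65 or over. If a table of under 65 against 65 or over is needed for regulatory format, keep it alongside as counts.

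The cost is a short change of SAP wording and one filter in the program, with no new data. The reference group becomes smaller and the intervals slightly wider. If all groups had the same rate, the standard error of the risk difference would grow by the factor √[(1/n + 1/(100 − n)) / (1/n + 1/(200 − n))]: about 3% for n = 10, 6% for n = 20 and 15% for n = 40.

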# 7.2.1. Inclusion criteria

- 1. Patients who have not developed invasive fungal infections at the time of initiation of administration of this product (patients with medical history of invasive fungal infections can be registered)
- 2. Patients with history of hematopoietic stem cell transplantation or patients who plan to receive hematopoietic stem cell transplantation

The indications and dosage and administration of this product are as follows. The latest package insert should be referred to when administering this product.

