8.1.3. Analysis of Binary Data

The frequency and proportion will be calculated. If the confidence interval of proportion is calculated, two-sided 95% confidence interval (exact method) will be calculated.

If the proportion is compared between subgroups, risk ratio and its 95% confidence interval, and risk difference and its 95% confidence interval will be calculated. In addition, risk ratio and its 95% confidence interval will be graphically presented (see Appendix 2). If the number of patients in at least one category compared is \leq 5, the number of patients and proportion will be calculated but risk ratio and its 95% confidence interval, and risk difference and its 95% confidence interval will not be calculated.

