8.2.2. Patient Background and Treatment History of Vfend

• Patient background

In the safety analysis set and effectiveness analysis set, the following patient background factors will be tabulated in accordance with Section 8.1.

- Sex [male, female]
- Age (years; continuous)
- Age [<15 years, ≥ 15 to <65 years, ≥ 65 years]
- Age (children 1) [newborns (<1 month after birth), infants (≥1 month to <1 year), younger children (≥1 to <7 years), children (≥7 to <15 years)]
- Age (children 2) [≤ 2 years, ≥ 2 to ≤ 15 years]
- Age (adults) [≥15 to <20 years, ≥20 to <40 years, ≥40 to <65 years, ≥65 to <70 years, ≥70 to <75 years, ≥75 years]
- Hospitalized status [inpatient, outpatient]
- Body weight (kg; continuous)
- Objective of treatment [primary prophylaxis (patients without history of fungal infection), secondary prophylaxis (patients with history of fungal infection), others]
- Details of other objectives of treatment

- Type of transplantation [autograft, allogeneic full transplantation, allogeneic mini-transplantation]
- Source of transplantation [bone marrow, cord blood, peripheral stem cell]
- Occurrence of GVHD (graft versus host disease) [absent, present]
- Indication for transplantation [leukemia, myelodysplastic syndrome, malignant lymphoma, myeloma, others]
- Severity of indication for transplantation [mild, moderate, severe]
- Hepatic dysfunction [absent, present, unknown]
- Severity of hepatic dysfunction [mild, moderate, severe, unknown]
- Renal dysfunction [absent, present, unknown]
- Severity of renal dysfunction [mild, moderate, severe, unknown]
- Past medical history [absent, present]
- Concurrent illness [absent, present]
- Concurrent congenital severe immunodeficiency [absent, present]
- White blood cell count before administration [$<3000/\mu$ L, $\geq 3000/\mu$ L]
- Neutrophil count before administration [$<500/\mu$ L, $\geq 500/\mu$ L]
- Concomitant use of immunosuppressants (other than steroids) [absent, present]
- Concomitant use of steroids [absent, present]
- Concomitant use of steroids or immunosuppressants other than steroids [absent, present]
- Use of contraindicated concomitant medications [absent, present]
- Use of concomitant medications requiring precautions for coadministration [absent, present]
- Concomitant use of other antifungal agents [absent, present]
- Concomitant use of broad-spectrum antibiotics [absent, present]
- Prior treatment (antifungal agents administered for prophylaxis of invasive fungal infections)

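### The subgroup labelled congenital severe immunodeficiency can, on the plainest reading of its definition, include acquired cases, so its risk ratios may describe a mixed group

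*SAP*

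**What the plan says.** SAP 5.4 lists the factor as "Congenital severe immunodeficiency² [absent, present"]. Its footnote gives the operational rule: "Congenital severe immunodeficiency is defined as a complication included in MedDRA HLGT 'congenital immune system disorders' and 'immunodeficiency syndrome' (primary and secondary"). The footnote does not say whether a term must lie in either MedDRA group or in both, does not explain the parenthesis, and gives no severity criterion.

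The factor is used in four places:

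- **Background tables (SAP 8.2.2).** It appears as "Concurrent congenital severe immunodeficiency [absent, present"] for both analysis sets. It is also broken down by SOC and PT, but only in the safety analysis set.
- **Safety (SAP 8.2.3.4).** "The number and proportion of patients who experienced at least one adverse drug reaction will be tabulated for each factor specified in Section 5.4", followed by the SAP 8.1.3 comparison.
- **Effectiveness (SAP 8.2.4.4).** The infection rate and the success rate are compared "in accordance with Section 8.1.3 for each of the factors specified in Section 5.4".
- **Screening (SAP 8.2.3.5 and 8.2.4.5).** A factor whose risk ratio is at least 2 or at most 0.5 gets further tables or listings.

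SAP 8.1.3 adds a size limit. "If the number of patients in at least one category compared is" five or fewer, "the number of patients and proportion will be calculated but risk ratio and its 95% confidence interval" are not both reported: the counts and proportion remain, while the risk ratio, the risk difference and their intervals are dropped.

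Protocol 7.2.1 sets the population: "Patients with history of hematopoietic stem cell transplantation or patients who plan to receive hematopoietic stem cell transplantation".

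**The concern.** The label and the rule do not match. Secondary immunodeficiency is acquired, so a rule that admits it reaches patients whom the word congenital excludes. The word severe has no counterpart in the rule at all.

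The mismatch matters more here than in most populations. The transplant indications named in SAP 5.4 are leukaemia, myelodysplastic syndrome, malignant lymphoma and myeloma, plus a category for others, and immunosuppressant use is recorded for all patients. An acquired immunodeficiency could plausibly be entered under complications (Protocol 7.3.1, item 10). The protocol lists no separate field for congenital immunodeficiency that would keep the two apart.

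Three outputs are at stake: the reported number of patients in a special population, the risk ratios and risk differences printed against the congenital label, and whether the factor passes the risk-ratio screen. Identifying factors that affect safety and effectiveness is a stated objective (Protocol 6, SAP 2.2), and the final analysis supports the re-examination application (SAP 3).

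**Working it through.** **Step 1. What the footnote admits under each reading.** Two points of wording are open: how the two groups are combined, and what the parenthesis means.

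| Combination | Parenthesis means type of immunodeficiency | Parenthesis means MedDRA primary and secondary classification |
|---|---|---|
| Union (a term in either group) | Acquired terms expressly included | Nothing limits the second group to congenital terms |
| Intersection (a term in both groups) | Acquired terms need not enter | Acquired terms need not enter |

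Only intersection avoids the mismatch. Reading the parenthesis as a coding matter does not avoid it by itself. No cell supplies a criterion for severe. The contents of each MedDRA group are not in the documents, so the exact terms cannot be checked here.

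**Step 2. Whether another section settles it.** SAP 8.2.2 repeats the label without narrowing it, and SAP 8.2.3.4 and 8.2.4.4 simply refer back to SAP 5.4. The footnote stands alone.

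**Step 3. Size.** The plan states no figure for this subgroup, so there is nothing to reproduce. What follows is illustration on assumed inputs.

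Let c be the number of congenital cases with risk ratio R, and a the number of acquired cases with risk ratio A, both relative to patients with neither. The expected ratio for the mixed group is

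(c × R + a × A) / (c + a).

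Take A = 1 first (acquired cases at reference risk):

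| c | a | R | Calculation | Mixed ratio |
|---|---|---|---|---|
| 10 | 3 | 2 | (20 + 3)/13 | 1.77 |
| 6 | 6 | 2 | (12 + 6)/12 | 1.50 |
| 6 | 20 | 2 | (12 + 20)/26 | 1.23 |
| 6 | 40 | 2 | (12 + 40)/46 | 1.13 |
| 3 | 40 | 2 | (6 + 40)/43 | 1.07 |
| 10 | 10 | 3 | (30 + 10)/20 | 2.00 |
| 10 | 20 | 3 | (30 + 20)/30 | 1.67 |

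With A = 1, a true ratio of exactly 2 falls below the screen as soon as any acquired case is added. A true ratio of 3 still reaches 2.00 when half the group is acquired.

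The bias need not be towards 1. If congenital cases carry the reference risk (R = 1) and acquired cases have A = 3, then c = 6 and a = 20 give (6 + 60)/26 = 2.54. The congenital label would be flagged with no congenital effect behind it.

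These are expected values. They ignore sampling error, which would be large in groups of this size.

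**Step 4. The size limit in SAP 8.1.3.** With 3 congenital cases alone, no ratio is given. With 3 congenital and 3 acquired cases the group is 3 + 3 = 6, and a ratio is printed.

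**The case against.** The strongest reply is that the footnote is unclear, not shown to be wrong. Under intersection acquired cases need not enter, and the SAP does not rule that reading out. This stands as far as it goes. It does not remove the point, because two programmers could build different groups from the same sentence and the more natural reading gives the mislabelled one.

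Second, a reader might infer that transplant patients in general will be classed as congenital. The documents do not support that. A patient enters only if a qualifying complication is recorded and coded. Being transplanted or immunosuppressed is not enough, and steroid and immunosuppressant use have their own factors in SAP 5.4. Nothing in the documents shows how many acquired cases would be recorded.

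Third, the SOC and PT table in SAP 8.2.2 would name any acquired terms, and SAP 9 provides a patient listing. This is a real safeguard. However, the table covers the safety analysis set only, and it does not change the risk ratios, the size limit or the screen.

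Fourth, the stakes are limited. SAP 4.1 treats all tests as exploratory with no significance level, SAP 4.2 has no decision rules, this is one of about 30 factors, and no main estimate depends on it. All of that is correct.

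**Conclusion.** The point holds in a limited form. On its plainest reading, footnote 2 admits acquired immunodeficiency to a group labelled congenital and severe, and no other section narrows it. The present group may therefore be mixed. If it is, the exploratory ratios and differences for this factor, the decision under SAP 8.1.3 to print them, and the screen result cannot be attributed to congenital immunodeficiency.

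The size is unknown. The case numbers (3 to 10 congenital, 3 to 40 acquired) and the risk ratios used above are assumptions, and the direction of the bias depends on the risk in acquired cases.

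Two stronger conclusions are tempting but go too far. One is that the ratio describes the wrong group. The documents support only that the group may be mixed, and under intersection it need not be. The other is that the size limit in SAP 8.1.3 is defeated. That rule counts whatever categories are compared and works as written; the weakness lies in the category it is given.

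The main safety and effectiveness estimates are unaffected.

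**What to change.** Amend SAP 5.4, footnote 2, in a dated revision before the final analysis:

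1. State that the factor counts only congenital or primary immunodeficiency terms.
2. Say whether the two HLGTs are combined by union or by intersection, and what the parenthesis means.
3. Define severe, or drop the word from the label.
4. Fix the list of qualifying terms before the final analysis is run.
5. If acquired immunodeficiency is of interest, give it its own absent/present factor under its own name.

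If the sponsor intends the mixed group, the alternative is to keep the rule and rename the factor immunodeficiency (congenital or acquired), here and in SAP 8.2.2.

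The cost is one footnote and one term list, with no new data collection. The downside of the restriction is that the congenital group may have five or fewer patients, in which case SAP 8.1.3 gives counts and proportions only.
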